8.2 Secondary outcome analysis

The secondary outcome of change in NPI-Q distress score from baseline survey to 6-month follow-up survey for intervention and control cohorts is compared using a difference-in-differences model with a linear distribution and identity link. Models adjusted for differences in demographic characteristics (race, ethnicity, age) and PHQ-8 at baseline. A point difference of 2 or greater on the NIPQ-Distress scale is generally considered to be clinically meaningful; therefore a difference in differences estimate of 2 or more in this model (i.e., a relative difference of 2 points or more between Intervention and Controls) would suggest a meaningful impact of the Intervention.

We hypothesized a relative decrease in NPI-Q distress in the Intervention group as compared to Controls.

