7.1.2 Clinical Outcome Cohort

For the NPI-Q Distress outcome measurement, the validated cohort was restricted to baseline and follow-up survey respondents with completed NPI-Q Distress measures (Intervention n=35, Control n=28). (See Figure 1 of cohort flowchart)

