7.2 General considerations for statistical analysis

Data are summarized by treatment group. Continuous variables are summarized using mean and standard deviations. Categorical variables are summarized using frequency and percentages. SAS Enterprise Guide 7.1 is used for analyses.

Demographic and other baseline characteristics are compared between groups. Race, ethnicity, age, gender, language, marital status, baseline primary care provider (PCP) utilization per member per month (PMPM), baseline inpatient utilization PMPM, baseline ED utilization PMPM, and baseline observation visits PMPM are summarized for the Utilization Outcome Cohort. For the Clinical Outcome Cohort, the same characteristics will be summarized, as well as NPI-Q Distress (caregiver distress), NPI-Q Severity (patient symptom severity), PHQ-8 (caregiver depression), and Quick Dementia Rating Scale (patient dementia severity) from the baseline survey.

A combination of t-tests (at $p < .05$), chi square tests (at $p < .05$) and standardized mean differences (cutoff of .15 or greater) were used to identify differences between cohorts and covariates for risk adjusted models. Based on these criteria, race, ethnicity, and age were identified as different between intervention and control in the Utilization Outcome Cohort, as were baseline PCP visits, inpatient hospitalizations, and Observation visits. For the Clinical Outcome Cohort, PHQ-8 (caregiver depression) was different across Intervention and Control. Risk adjusted models for clinical outcomes also adjusted for the demographic characteristics (race, ethnicity, and age) identified for the risk adjusted utilization models in order to maintain consistency across models.

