8 STATISTICAL ANALYSES

8.1 Primary outcome analysis

The change in ED visits PMPM from 12 months prior to training to 6 months post-training for intervention and control cohorts are compared using a differences-in-differences model with a negative binomial distribution (to account for utilization count data) and log link. This model estimates a difference-in-differences rate ratio that provides an estimate of the relative rate reduction/increase in ED visits PMPM in the intervention group as compared to controls.

Models included a weight for the number of member months in the pre and post periods, allowing PWD with more member months (and therefore more stable estimates) to contribute more strongly to the intervention effect. The training (“enrollment”) month was not included in either pre or post period. Models adjusted for baseline utilization and demographic characteristics (race, ethnicity, age) that differed across intervention and control cohorts. A sensitivity analysis removed PWD who died in the post period.

We hypothesized high feasibility in measuring ED visits for this population but had no specific hypothesis regarding whether the program would impact ED utilization in the relatively short 6 month-post period.

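### SAP 8.2 reads a 2-point NPI-Q Distress estimate as meaningful with no confidence interval and no sign; whether that is strict or weak depends on an SD the documents do not give

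*SAP*

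**What the plan says.** SAP 8.2 compares the change in NPI-Q Distress from baseline to the 6-month survey between arms, using a linear difference-in-differences model. It takes a 2-point difference on the scale as clinically meaningful and continues: "therefore a difference in differences estimate of 2 or more in this model". A parenthesis restates this as a relative difference between the arms, again without a sign. The sentence concludes that such an estimate "would suggest a meaningful impact of the Intervention". The direction comes in a separate sentence: "We hypothesized a relative decrease in NPI-Q distress in the Intervention group as compared to Controls".

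On adjustment, SAP 8.2 says "Models adjusted for differences in demographic characteristics (race, ethnicity, age) and PHQ-8 at baseline". It does not say whether the model is fitted to change scores or to stacked pre and post records, and it does not mention the nurse random effects that protocol 9.4 specifies.

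Neither document specifies a confidence interval or test level for this outcome. The only level in the SAP, p < .05 in section 7.2, belongs to the baseline comparisons, which "were used to identify differences between cohorts and covariates for risk adjusted models". SAP 7.1.2 gives the analysed cohort as 35 Intervention and 28 Control caregivers. SAP 2.3 gives the scale range as 0 to 60.

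**The concern.** That a 2-point difference matters clinically does not show that an observed 2-point estimate can be told apart from no difference. SAP 8.2 moves from the first to the second in one sentence, and nothing in it asks how precise the estimate is.

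The sentence carries some weight. For ED visits, SAP 8.1 says the team "had no specific hypothesis regarding whether the program would impact ED utilization". Of the two outcome analyses in SAP section 8, only NPI-Q Distress has a directional hypothesis and a stated threshold for a program effect. Followed as written, the rule could turn an estimate compatible with no effect into a positive statement. Protocol 9.2 also wants the pilot to inform effect sizes for a full-scale study, and an effect size without its precision serves that purpose poorly.

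The missing sign is a smaller drafting point. If the estimate is Intervention minus Control, benefit is negative, and a literal reading of the threshold is met by a relative increase in distress.

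**Working it through.** **Inputs.** From the documents: 35 and 28 caregivers (SAP 7.1.2), a 2-point threshold (SAP 8.2) and 30 nurses (SAP 3). Assumed here because the documents give no value: the SD of the change score, a two-sided 95% level, the nurse ICC and the variance explained by covariates.

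**The plan's own figure.** Protocol 9.3 expects 37 caregivers per arm with both surveys. 150 × 0.5 = 75 per survey, and 75 × 0.5 = 37.5 for both, so the figure reproduces. The 35 and 28 obtained are somewhat fewer. No SD, power or test level accompanies it.

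**Standard error.** For an unadjusted comparison of change scores between independent caregivers with equal variances:

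SE = SD × √(1/35 + 1/28) = 0.2535 × SD

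**Break-even SD.** With t(0.975, 61 df) = 1.9996, a 2-point estimate excludes 0 only if

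SD < 2 / (1.9996 × 0.2535) = 3.94

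**By assumed SD.** The last column is the normal tail probability beyond 2/SE when the true effect is nil. It counts the benefit direction only; double it for either direction.

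| SD of change | SE | 95% CI around -2 | Chance of -2 or lower |
|---|---|---|---|
| 3 | 0.761 | -3.52 to -0.48 | 0.4% |
| 4 | 1.014 | -4.03 to 0.03 | 2.4% |
| 6 | 1.521 | -5.04 to 1.04 | 9.4% |
| 8 | 2.028 | -6.06 to 2.06 | 16.2% |
| 10 | 2.535 | -7.07 to 3.07 | 21.5% |

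**An estimate of 0.** The interval also matters here. At SD 3 it is -1.52 to 1.52, which excludes 2 points both ways. At SD 6 it is -3.04 to 3.04, which excludes neither.

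**Nurse clustering.** 63/30 = 2.1 caregivers per nurse, so the design effect is 1 + 1.1 × ICC: 1.055 at ICC 0.05 and 1.11 at ICC 0.10. On 28 nurse-level df (30 nurses minus 2 arms) the unclustered limit is 3.85. Dividing by √1.055 and √1.11 gives 3.75 and 3.66, so about 3.7.

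**Covariates.** In a change-score regression, covariates explaining an assumed 20% of the variance would raise the limit on the raw SD to 3.94/√0.80 = 4.41. That gain need not occur in a stacked model: with complete pairs, baseline covariates entered as main effects leave the difference-in-differences estimate unchanged.

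**The case against.** The wording is soft. It offers a size benchmark and claims no test, for a secondary outcome in a pilot whose primary objective is feasibility and which makes no power claim. A linear model produces a standard error and interval as routine output, and SAP 8.1 names no interval for the ED rate ratio either, so the omission may be one of general reporting detail. The direction is in the very next sentence. The larger chance rates need SDs of 6 to 10, for which the documents give no support; at an assumed SD of 3 the benchmark is strict.

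Most of this stands and limits the severity. It does not remove the point. SAP 8.2 does more than leave an interval unnamed: it states how the estimate is to be read, and that reading uses the point estimate alone. An interval printed beside it would not alter the rule, because -2 with an interval that includes 0 would still meet it.

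A reader might go further in three ways, none of which the documents support:

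- That SAP 8.2 sets a formal success criterion or means to suppress the interval. Its language is interpretive, and nothing in the SAP withholds precision.
- That the plan would count worsening as success. The hypothesised decrease is stated; it is only not joined to the threshold.
- That 35 and 28 caregivers cannot support a 2-point finding. Below an SD of about 3.9 they can.

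**Conclusion.** The point holds in a limited form. SAP 8.2 attaches a statement of meaningful impact to an unsigned point estimate, with no interval. Whether 2 points can be told apart from 0 turns on an SD of change of about 3.9, or about 3.7 with nurse clustering at an ICC of 0.05 to 0.10. The documents give no SD, so the harm is conditional: the same rule is strict at an SD of 3 and weak at 8 or 10. The figures also assume complete pairs, equal variances, a two-sided 95% level and, for the main limit, no covariate adjustment.

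Severity is minor to moderate, given the soft wording, the secondary outcome and the pilot purpose. It might be inferred that no positive statement should be allowed unless the interval excludes 0. That does not follow: such a gate would turn a pilot meant to supply effect-size data into a significance test that neither document sets out.

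**What to change.** Reword the benchmark in SAP 8.2 along these lines:

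> The estimate is the change in Intervention minus the change in Control; negative values favour Intervention. The benchmark is a relative decrease of 2 points or more (-2 or lower). A value of +2 or higher will be reported as possible worsening. The estimate will be given with a two-sided 95% CI that accounts for the two measurements per caregiver (by change scores, or by a caregiver effect if records are stacked) and for clustering by nurse as in protocol 9.4. The benchmark will be interpreted with the CI, stating whether it includes 0, -2 and +2. The point estimate alone will not support a statement of impact.

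Both parts of the variance clause are needed: with stacked records, a nurse effect alone leaves out the correlation within caregiver. No new descriptive summary is required, since SAP 7.2 already says "Continuous variables are summarized using mean and standard deviations", which can be read to cover the change score. Exclusion of 0 should not become a formal success gate.

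The cost is one wording change and an interval from data already collected. A positive statement becomes slightly harder to make. SAP 6 to 7.2 already report cohort sizes and covariate choice in the past tense, so if outcome results were known when the change is made, it should be dated and labelled post hoc.

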9 ADVERSE EVENTS

There were no adverse events, serious adverse events or significant protocol deviations.

Figure 1. Cohort Flowchart
